## 16.0 Statistical Considerations and Methodology

### 16.1 Overview

This is a Phase I/II, single-arm, open-labeled, multi-center study of pembrolizumab in combination with binimetinib in women with unresectable locally advanced or metastatic triple negative breast cancer. The main objective of this study is to assess the safety and efficacy of the combination of pembrolizumab and binimetinib.

The phase I part will be a dose-finding study, utilizing the classic 3+3 study design. The primary objectives are to determine the DLTs, to evaluate the safety of this combination, and to establish the recommended dose for the phase II part. There are a total of 2 dose levels as defined in the treatment section. The number of participants enrolled in the phase I of this study will range from 6-12 participants.

#### 16.11 Primary Endpoint

##### 16.111 Phase I

The primary endpoint in the phase I portion is to determine the maximum tolerated dose of this combination.

##### 16.112 Phase II

The primary endpoint in the phase II portion is confirmed objective response rate (ORR) by RECIST criteria with pembrolizumab and binimetinib.

We will utilize Simon's Two-Stage Optimal Design to test the null hypothesis that this two-drug combination has an ORR of at most 15% versus the alternative hypothesis that it has an ORR of at least 35%. Patients in the phase I part who are treated with the recommended dose of phase II and are evaluable for response will be included in the phase II analysis. The first stage will require 9 evaluable patients. With this design, if  $\leq 1$  of the first 9 patients has objective response (i.e. CR or PR), the study will be closed since there is sufficient evidence that the therapy is not promising. Otherwise, an additional 14 patients will be enrolled. In total, if  $> 5$  patients of 23 patients have objective response, this combination will be considered promising. This design has 80% power while controlling the type I error at 10%. Under the null hypothesis (when the true objective response rate is 15%), this design has a 60% chance of stopping the trial early. A minimum of 9 and a maximum of 23 evaluable patients are required to evaluate the primary endpoint. To account for cases that are ineligible or non-evaluable, we will accrue an additional 3 patients for a maximum accrual of 26 patients in this phase. The secondary endpoints in part II include objective response rate by irRECIST, progression free survival, and overall survival.

### 16.2 Sample size and accrual rate

For phase I, the study will require 6-12 patients to complete, allowing for 6 patients per dose level and 2 predefined dose levels. In phase II, the study will require 9-26 patients to complete. Therefore, the total sample size for this study is 15-38 patients. At an anticipated accrual rate of 10-12 patients/year, we expect that this trial will need to accrue patients for anywhere from 15 to 32 months.

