**Phase II (includes all phase II patients including phase I patients treated at the MTD):**

Accrual will be temporarily suspended to this study if at any time we observe events considered at least possibly related to study treatment (i.e. an adverse event with attribute specified as “possible,” “probable,” or “definite”) that satisfy either of the following:

- If 3 or more patients in the first 9 treated patients experience a Grade 4 or higher adverse event at least possibly related to treatment.
- If after the first 9 patients have been treated, 25% of all patients experience a Grade 4 or higher adverse event at least possibly related to treatment.

We note that we will review Grade 4 and 5 adverse events deemed “unrelated” or “unlikely to be related”, to verify their attribution and to monitor the emergence of a previously unrecognized treatment-related adverse events.

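### Section 16.2 totals Phase I and Phase II as if no patient were shared (15-38), although 16.112 carries Phase I patients into the Phase II analysis; the accrual time does not fit 38 either

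*Combined protocol and SAP*

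**What the plan says.** Section 16.2 gives Phase I as 6-12 patients (6 at each of two dose levels) and continues: "In phase II, the study will require 9-26 patients to complete. Therefore, the total sample size for this study is 15-38 patients". It expects accrual of 10 to 12 patients a year and a duration of 15 to 32 months. The table in 16.64 uses 38 as the accrual target.

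Section 16.112 sets up the Simon two-stage design. Phase I patients who received the dose chosen for Phase II and "are evaluable for response will be included in the phase II analysis". On the stages it says "The first stage will require 9 evaluable patients"; with at most 1 responder among them, accrual ends. Otherwise 14 more are enrolled, and more than 5 responders of 23 counts as promising. It adds: "A minimum of 9 and a maximum of 23 evaluable patients are required to evaluate the primary endpoint". Three further places, 26 in all, allow for ineligible or non-evaluable cases.

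Section 16.41 plans 6 patients at the MTD. The Phase II adverse event stopping rule in 16.52 "includes all phase II patients including phase I patients treated at the MTD".

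**The concern.** A patient treated at the recommended dose in Phase I counts once as a person but twice in the 16.2 total: among the 6-12 and again among the 9-26. The stated sample size therefore does not describe the design in 16.112. The same figure feeds the accrual target in 16.64, and the duration in 16.2 does not fit it.

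At stake are up to 6 patients beyond what the two-stage design needs, and an accrual forecast that cannot be right for the stated total. The plan does not say that carried-over patients reduce the number of new Phase II registrations. Nor does it say which 23 patients decide the result if more than 23 are evaluable. In an open-label, single-arm trial that choice should not be left until responses are known.

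**Working it through.** **Inputs.** Phase I 6-12 and Phase II 9-26 (16.2); 6 patients at the MTD (16.41); stage 1 of 9 with stop at 1 or fewer, final cut-off above 5 of 23, null ORR 15%, alternative 35%, type I error 10%, power 80%, early stopping 60% under the null (16.112); 10-12 patients a year and 15-32 months (16.2).

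**1. The stated design reproduces.** For final size n and true rate p,

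P(promising) = sum over x = 2 to 9 of P(Bin(9, p) = x) × P(Bin(n − 9, p) ≥ 6 − x).

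- n = 23, p = 0.15: 0.0990.
- n = 23, p = 0.35: 0.8037.
- Early stop at p = 0.15: 0.85^9 + 9 × 0.15 × 0.85^8 = 0.2316 + 0.3679 = 0.5995.

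These match the stated 10%, 80% and 60%.

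**2. The stated total.** 6 + 9 = 15 and 12 + 26 = 38. The sums are correct, but no shared patient is subtracted.

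**3. The total with overlap.** Let k be the number of evaluable Phase I patients carried over.

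- Minimum: 6 + (9 − k) = 15 − k.
- Maximum: 12 + (26 − k) = 38 − k.
- k = 6: 9 and 32. New Phase II enrolment is then at most 26 − 6 = 20.
- k = 0: 15 and 38, the stated figures.

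**4. Accrual time.** Months = patients ÷ yearly rate × 12.

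| Patients | At 12 a year | At 10 a year |
|---|---|---|
| 9 | 9.0 | 10.8 |
| 15 | 15.0 | 18.0 |
| 32 | 32.0 | 38.4 |
| 38 | 38.0 | 45.6 |

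The upper limit of 32 months is too short for 38 patients even at the faster rate. At 12 a year it matches 32 patients, which is 12 + 26 − 6. The lower limit of 15 months matches 15 patients at the same rate, with no overlap. So the two ends of the stated duration fit two different counts.

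**5. What surplus patients would do to the test.** Keep stage 1 at 9, the final cut-off at more than 5, and p = 0.15, and let n grow:

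| n analysed | Type I error |
|---|---|
| 23 | 9.9% |
| 24 | 11.3% |
| 26 | 14.1% |
| 29 (6 + 23) | 18.4% |

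The design has almost no slack: one surplus evaluable patient takes type I error above the stated 10%.

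**The case against.** The best defence is that the overlap is intended and 38 is only a cautious ceiling. The 16.52 stopping rule counts Phase I patients at the MTD within the Phase II set, and therefore among its first 9. The 32-month limit fits a count with overlap. Carry-over also depends on being evaluable for response, so k is not known in advance and the total approaches 38 when few carry over. The last part stands: 9-32 rests on k = 6. It does not rescue the text, because 15-38 holds only if nobody carries over, and 32 months contradicts 38 patients in either case.

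A reader might go further and infer that the trial runs at a type I error of 18% to 22%, by analysing 29 patients (18.4%) or 32 (22.4%) against the cut-off of more than 5. The documents do not support this. Section 16.112 words the interim rule on the first 9, words success as a count out of 23, and limits the primary endpoint to 23 evaluable patients. Reaching 32 would also need all three spare places to yield evaluable patients, although they are there to cover those who are not. Reading stage 1 on 15 patients (6 carried over plus 9 new) likewise conflicts with a rule set on the first 9.

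**Conclusion.** The total in 16.2, the target in 16.64 and the accrual duration need correcting. With 6 evaluable carry-overs, the design in 16.112 implies 9-32 patients rather than 15-38. Each carry-over fewer than 6 raises both limits by one. Phase I replacements are not counted.

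The primary test is sound as 16.112 words it: 9.9% type I error and 80.4% power at 23 evaluable patients. Inflation is a conditional risk only. The 18.4% at n = 29 would require carried-over patients on top of full Phase II accrual, all of them analysed, and an unchanged cut-off. A smaller gap remains even when overlap is counted properly: 26 accrued patients could yield more than 23 evaluable, and the plan does not say which 23 decide.

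**What to change.** - In 16.112 and 16.2, state that evaluable Phase I patients treated at the recommended dose fill places among the 9, the 23 and the 26, so that new Phase II enrolment is 26 minus the number carried over.
- In 16.2, restate the total as 9-32, with the assumption of 6 evaluable carry-overs and Phase I replacements excluded. Change the 16.64 target to match.
- Recompute the duration from the same counts. For 9-32 patients at 10-12 a year it runs from 9 months (9 patients at 12 a year) to about 38 months (32 patients at 10 a year).
- State that the stage 1 and final decisions use the first 9 and the first 23 evaluable patients in registration order.

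The cost is a wording amendment and no added patients. The downside is up to 6 fewer patients for the secondary and biomarker summaries.

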### 16.3 Statistical Analysis Plan

The objective of the phase I portion of the study is to estimate the maximum tolerated dose (MTD) using the standard 3+3 design. Safety/adverse events data will be tabulated, including adverse events of all grades.

For the phase II portion of the study, the overall response rate by RECIST will be estimated using the approach of Jung and Kim [On the estimation of the binomial probability in multistage clinical trials. Stat Med 23:881-96, 2004]. The 90% lower confidence bound will be calculated using the approach of Koyama and Chen [Proper inference from Simon's two-stage designs. Stat Med 27:3145-54, 2008]. Secondary efficacy endpoints include objective response rate by immune-related response criteria (irRECIST), progression-free survival (PFS) and overall survival (OS). Objective response rate by irRECIST will be estimated as a binomial proportion with a 2-sided 95% CI. PFS will be defined as the time from study enrollment to date of progression. Patients who have not progressed (including those lost to follow-up) at the time of data analysis will be censored at the date last known to be free of progression. OS will be defined as the time from study enrollment to death attributable to any cause (i.e. death from breast cancer, non-breast cancer cause, or from unknown cause). Patients who are alive (including those lost to follow-up) at the time of data analysis will be censored at the last known alive date. A Kaplan-Meier curve will be used to summarize the PFS and OS experience of this patient cohort.

Baseline TILs and percent change in TILs from baseline will be summarized. Logistic regression models will be used to assess the correlation between these biomarkers and ORR in order to assess their prognostic significance. Cox Proportional Hazard models will be used to assess their correlation with time-to-event endpoints such as PFS and OS. Similar analyses will be performed for other exploratory biomarkers such as immune related gene signature, PDJ amplification, etc. These analyses will be exploratory in nature. As such, no adjustment for multiple comparisons will be made; all hypothesis tests will be based on 2-sided alpha = 0.05 level.

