**2.2 Secondary Goals**

2.21 To evaluate the safety and tolerability of binimetinib in combination with pembrolizumab.

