## 10.6 Required Routine Reporting

### 10.61 Baseline and Adverse Events Evaluations

Pretreatment symptoms/conditions to be graded at baseline and adverse events to be graded at each evaluation. (Grading is per CTCAE v4.0 **unless** alternate grading is indicated in the table below):

CTCAE SYSTEM ORGAN CLASS	Adverse event/Symptoms	Baseline	Each evaluation
Blood and lymphatic system disorders	Febrile neutropenia	X	X
Eye disorders	Retinal detachment	X	X
	Retinal vascular disorder (RVO)	X	X
General disorders and administration site conditions	Fatigue	X	X
Gastrointestinal disorders	Nausea	X	X
	Vomiting	X	X

CTCAE SYSTEM ORGAN CLASS	Adverse event/Symptoms	Baseline	Each evaluation
	# of Stools	X	
	Diarrhea		X
	Constipation	X	X
Infections and infestations	Sepsis	X	X
Investigations	CPK (CK) increased	X	X
	Creatinine increased	X	X
	Neutrophil count decreased	X	X
	Platelet count decreased	X	X
Nervous system disorders	Peripheral sensory neuropathy	X	X
	Peripheral motor neuropathy	X	X
Skin and subcutaneous tissue disorders	Rash, acneiform	X	X
	Rash, maculo-papular	X	X
Vascular disorders	Hypertension	X	X

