#### 10.62 All other AEs

Submit via appropriate MCCC Case Report Forms (i.e., paper electronic, as applicable) the following AEs experienced by a patient and not specified in Section 10.6:

10.621 Grade 2 AEs deemed *possibly, probably, or definitely* related to the study treatment or procedure.

10.622 Grade 3 and 4 AEs regardless of attribution to the study treatment or procedure.

10.623 Grade 5 AEs (Deaths)

10.6231 Any death within 30 days of the patient's last study treatment or procedure regardless of attribution to the study treatment or procedure.

10.6232 Any death more than 30 days after the patient's last study treatment or procedure that is felt to be at least possibly treatment related must also be submitted as a Grade 5 AE, with a CTCAE type and attribution assigned.

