Overall, the risk for binimetinib to be a cause of or be affected by significant drug-drug interactions is predicted to be low. However, given the predominant role of UGT1A1 in the metabolism of binimetinib, special consideration should

be taken for co-administration of drugs that are UGT1A1 inhibitors or inducers, and administration of binimatinib to patients with low UGT1A1 activity.

Binimatinib has been shown to be a substrate for P-gp and BCRP in vitro. The impact of P-gp/BCRP inhibitors on the PK of binimatinib in vivo is unknown; therefore, it is recommended that P-gp and BCRP inhibitors are dosed with caution.

15.17 **Known potential toxicities:**

**Very Common (≥10%)** - Anemia, abdominal pain, constipation, diarrhea, nausea, vomiting, fatigue, peripheral edema, increased AST, increased ALT, increased blood creatine phosphokinase (CPK), dyspnea, dermatitis acneiform, pruritus, rash, hypertension

**Common (≥1% - <10%)** – Left ventricular dysfunction, tachycardia, chorioretinopathy, eye edema, macular edema, retinal detachment, retinopathy, blurred vision, visual impairment, dry mouth, gastritis, gastrointestinal obstruction, stomatitis, asthenia, facial edema, general physical health deterioration, generalized edema, malaise, mucosal inflammation, pyrexia, cellulitis, pneumonia, infection, decreased ejection fraction, increased GGT, increased INR, increased troponin T, dehydration, hyponatremia, arthralgia, muscular weakness, myalgia, cough, epistaxis, hypoxia, pulmonary embolism, alopecia, maculo-papular rash, skin fissures, hypotension

**Uncommon (≥0.1 - <1%)** - Left ventricular failure, retinal vein occlusion, retinal vein thrombosis, reduced visual acuity, enteritis, gastroenteritis, gastrointestinal hemorrhage, acute hepatic failure, irregular heart rate, increased troponin I, increased troponin T, hypoglycemia, myositis, dropped head syndrome, renal failure, atelectasis, lung infiltration, pneumonitis, pneumothorax, wheezing, angioedema, erythema nodosum/panniculitis, palmar-plantar dysesthesia syndrome, macular rash, deep vein thrombosis, hematoma

15.18 **Drug procurement:**

Binimatinib is supplied by Pfizer Inc. (formerly Array Biopharma LLC and Array Biopharma Inc.), Inc

15.19 **Nursing guidelines**

15.191 Instruct patient to take binimatinib twice daily approximately 12 hours apart. Agent may be taken with or without food.

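### Section 16.3 plans adverse event tables for all grades, but Section 10.6 requires all grades for only 18 terms, so all-grade rates of other expected toxicities would be biased downward

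*Combined protocol and SAP*

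**What the plan says.** Secondary goal 2.21 is "To evaluate the safety and tolerability of binimetinib in combination with pembrolizumab". The planned output is in Section 16.3, in the phase I paragraph: "Safety/adverse events data will be tabulated, including adverse events of all grades".

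Collection is set in Section 10.6. For a fixed list, 10.61 requires "Pretreatment symptoms/conditions to be graded at baseline and adverse events to be graded at each evaluation". The list has 18 terms graded at each evaluation: febrile neutropenia, retinal detachment, retinal vascular disorder, fatigue, nausea, vomiting, diarrhea, constipation, sepsis, CPK, creatinine, neutrophils, platelets, sensory and motor neuropathy, acneiform and maculo-papular rash, and hypertension.

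Everything else falls under 10.62, which covers "the following AEs experienced by a patient and not specified in Section 10.6". It names three categories: "Grade 2 AEs deemed *possibly, probably, or definitely* related to the study treatment or procedure"; "Grade 3 and 4 AEs regardless of attribution to the study treatment or procedure"; and Grade 5 events, meaning deaths within 30 days of the last study treatment or procedure, and later deaths if at least possibly treatment related.

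**The concern.** The planned tables and the collection rule do not match. For a term outside the 10.61 list, a table headed all grades would hold only part of the events, and an event that was never requested cannot be told apart from one that did not occur. The unlisted terms include much of the known toxicity of both drugs.

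The safety record of a new combination is at stake. Section 16.41 says that six patients at the MTD are enough to identify common toxicities there. That is harder when the lower grades of an expected toxicity are not requested. The protocol also acts on low grades: Table 8.2 has a row for Grade 1-2 left ventricular dysfunction, and Table 8.31 has rows that start at Grade 2 for liver tests, pneumonitis and colitis.

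**Working it through.** The plan states no adverse event rate, so there is no figure to reproduce. The check compares the sections and then illustrates the size.

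**1. What must be recorded**

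| Event | The 18 terms in 10.61 | Any other term (10.62) |
|---|---|---|
| Grade 1 | yes | no item |
| Grade 2, unlikely or unrelated | yes | no item |
| Grade 2, at least possibly related | yes | yes |
| Grade 3-4 | yes | yes, any attribution |

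**2. Expected toxicities that are not on the list**

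- Very common, at least 10%: AST and ALT increased and anemia with binimetinib (15.17, for example "increased AST, increased ALT, increased blood creatine phosphokinase (CPK), dyspnea"); pruritus with both drugs (15.17, 15.27).
- Common, 1% to below 10%: decreased ejection fraction with binimetinib (15.17); hypothyroidism, hyperthyroidism, pneumonitis and colitis with pembrolizumab (15.27).

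**3. Other routes into the database**

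- Section 10.1(f) puts expedited events onto the routine forms, and the table in 10.41 makes Grade 1-2 events expedited when they lead to hospitalization of at least 24 hours. This route is real but narrow.
- The calendar in 4.1 waives entry of laboratory forms in RAVE only for the Retreatment Phase, which implies that laboratory values are entered during initial treatment. No section derives adverse event grades from them, and they could not recover pneumonitis, colitis or pruritus.
- Section 18.1 refers to a case report form packet that is not among the documents.

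**4. Illustration of size**

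Let s1 and s2 be the shares of affected patients whose worst grade is 1 or 2, and u the share of those Grade 2 events judged unlikely or unrelated. None of the three is in the documents; the assumed ranges are s1 30% to 70%, s2 20% to 40% and u 0% to 50%.

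Recorded rate = true rate × (1 − s1 − s2 × u).

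- Mild case: 1 − 0.30 − 0.40 × 0 = 0.70 captured.
- Middle case: 1 − 0.50 − 0.30 × 0.25 = 0.425 captured.
- Severe case: 1 − 0.70 − 0.20 × 0.50 = 0.20 captured.

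The Grade 2 term removes 0, 7.5 and 10 percentage points, against 30, 50 and 70 for Grade 1, so the loss is mainly Grade 1.

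The chance of at least one recorded case among six patients is 1 − (1 − rate)^6. The maximum total sample is 38 (16.2). The true rates are also assumptions: 20% for a term listed at 10% or more, and 10% for the boundary between the two frequency bands.

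| True rate | Case | Recorded rate | Expected of 38 | At least one of 6 |
|---|---|---|---|---|
| 20% | all grades collected | 20% | 7.6 | 74% |
| 20% | mild | 14% | 5.3 | 60% |
| 20% | middle | 8.5% | 3.2 | 41% |
| 20% | severe | 4% | 1.5 | 22% |
| 10% | all grades collected | 10% | 3.8 | 47% |
| 10% | mild | 7% | 2.7 | 35% |
| 10% | middle | 4.3% | 1.6 | 23% |
| 10% | severe | 2% | 0.8 | 11% |

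**5. What does not change**

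Grade 3 and 4 events are collected whatever their attribution, and the accrual rules in 16.52 count related events of Grade 4 or higher. DLTs (7.421) must be at least possibly related, and nearly all criteria start at Grade 3 or higher. Of the exceptions, retinal vascular disorder is on the 10.61 list and related Grade 2 retinopathy is collected under 10.621. The ejection fraction criterion can be met by a fall that Table 8.2 labels Grade 1-2, but 7.413 requires any DLT to be notified to the Study Chair as soon as it occurs.

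**The case against.** The strongest reply is that 16.3 can be read more mildly: whatever is collected will be tabulated without a grade cut-off. On that reading no complete incidence is promised. The sentence allows this, but a table built that way still needs a label, because its reader cannot know that the lower grades were requested for some rows and not for others.

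The second reply is that the forms may ask for more than 10.62, and that laboratory grades could be computed from RAVE. Both are possible. Neither is planned in the text, and the second covers laboratory terms only.

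The third is that *possible* attribution is a low threshold (10.3), so most expected Grade 2 events in a single-arm trial would qualify. This stands, and it is why the loss is put mainly at Grade 1.

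A reader might also infer more than the documents support:

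- *That low grades outside the list are never captured.* The hospitalization route contradicts this.
- *That thyroid, lung or cardiac rates would be wrong by a large, known amount.* Section 15 lists those terms at 1% to below 10% as single-agent figures, and no grade mix is given.
- *That the list is arbitrary.* Constipation is very common with binimetinib (15.17), and peripheral neuropathy is a listed, uncommon toxicity of pembrolizumab (15.27).
- *That the MTD or the stopping rules are compromised.* They rest essentially on events that are collected or notified.

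**Conclusion.** The inconsistency holds on the plain text. If Sections 10.6 and 16.3 are followed as written, all-grade rates for the unlisted expected toxicities are biased downward, and the direction does not depend on any assumption. The size does. With an assumed Grade 1 share of 30% to 70%, about that share of affected patients would be missed; adding unrelated Grade 2 events takes the assumed severe case to 80%. These are illustrations and not estimates for this trial.

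The conclusion assumes that the unseen forms ask for no more than the protocol requires and that grades are not derived from laboratory values. The consequence is confined to the description of lower-grade toxicity under goal 2.21. It should be corrected, but it does not threaten the response endpoint.

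**What to change.** 1. In 16.3, tabulate all grades only for the 10.61 terms. Label all other terms *Grade 2 at least possibly related, and Grade 3 or higher*.
2. Add to 10.61, at baseline and each evaluation, the toxicities already open to observation under the study calendar: ALT, AST and bilirubin increased, anemia, ejection fraction decreased, hypothyroidism, hyperthyroidism, pneumonitis, colitis and pruritus. Bilirubin is only an uncommon listed toxicity (15.27), but it is in the chemistry panel and in the dose modification tables.
3. If terms are not added for the laboratory items, state that their grades will be derived from the values in RAVE. This does not replace solicited terms for pneumonitis, colitis or pruritus.

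The cost is one sentence in 16.3, a few more solicited terms on the forms and slightly more data entry, with no new procedure. If the forms can no longer change, step 1 alone stops uncollected events from being read as absent.

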2.22 To evaluate the ORR by immune-related RECIST criteria (irRECIST)

2.23 To evaluate the progression free survival (PFS), duration of response (DoR), and disease control rate (DCR) by RECIST and irRECIST.

2.24 To assess overall survival (OS).

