#### **Reportable categories of Death**

- Death attributable to a CTCAE term.
- Death Neonatal: A disorder characterized by cessation of life during the first 28 days of life.
- Death NOS: A cessation of life that cannot be attributed to a CTCAE term associated with Grade 5.
- Sudden death NOS: A sudden (defined as instant or within one hour of the onset of symptoms) or an unobserved cessation of life that cannot be attributed to a CTCAE term associated with Grade 5.

- Death due to progressive disease should be reported as **Grade 5 “Neoplasms benign, malignant and unspecified (including cysts and polyps) – Other (Progressive Disease)”** under the system organ class (SOC) of the same name. Evidence that the death was a manifestation of underlying disease (e.g., radiological changes suggesting tumor growth or progression: clinical deterioration associated with a disease process) should be submitted.

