### 11.1 Schedule of Evaluations

For the purposes of this study, patients should be reevaluated every 6 weeks. In addition to a baseline scan, confirmatory scans should also be obtained 4 weeks following initial documentation of objective response.

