#### 11.46 Symptomatic Deterioration

Patients with global deterioration of health status requiring discontinuation of treatment without objective evidence of disease progression at that time, and not either related to study treatment or other medical conditions, should be reported as PD and irPD due to "symptomatic deterioration." Every effort should be made to document the objective progression even after discontinuation of treatment due to symptomatic deterioration. A patient is classified as having PD and irPD due

to “symptomatic deterioration” if any of the following occur that are not either related to study treatment or other medical conditions:

- Unintentional weight loss >10% of body weight
- Decline in performance status of >1 level on ECOG scale

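### PFS counts progression only, so a patient who dies without documented progression is censored and PFS is overstated whenever such deaths occur

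*Combined protocol and SAP*

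**What the plan says.** PFS is a secondary goal under Section 2.2: "To evaluate the progression free survival (PFS), duration of response (DoR), and disease control rate (DCR) by RECIST and irRECIST".

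The definition is in Section 16.3: "PFS will be defined as the time from study enrollment to date of progression". Patients who have not progressed by the analysis, including those lost to follow-up, "will be censored at the date last known to be free of progression". Death is not mentioned in either sentence.

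The next definition in the same paragraph does mention it: "OS will be defined as the time from study enrollment to death attributable to any cause". On estimation, the section says: "A Kaplan-Meier curve will be used to summarize the PFS and OS experience of this patient cohort". PFS is also an outcome in the Cox models for TILs, the immune gene signature and PDJ amplification, which Section 16.3 calls exploratory.

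**The concern.** A patient who dies before progression is documented has no progression date and so falls under the censoring sentence. The text does not say outright that deaths are censored, but its two sentences leave no other place for them. Since the same paragraph names death as the OS event, a reader cannot assume it was meant for PFS as well.

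The quantity estimated is then time to progression under the name PFS. Kaplan-Meier estimation assumes that censored patients have the same future risk as those still followed, which cannot be true of patients who have died. In a single-arm trial PFS can only be read against outside data, where the reader will take the name to include death. Section 1.0 cites a median OS of 13 months for this disease, so deaths during follow-up are to be expected.

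**Working it through.** **Does any other section make death a PFS event?**

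- Section 11.46 classes symptomatic deterioration as PD and irPD. It applies to "Patients with global deterioration of health status requiring discontinuation of treatment without objective evidence of disease progression at that time", and it excludes decline related to study treatment or other medical conditions. Some patients are captured before death. Toxic and intercurrent deaths are not, nor are sudden deaths with no preceding decline that stopped treatment.
- Section 10.52 has a coding rule that begins "Death due to progressive disease should be reported as". It concerns Grade 5 adverse event reporting and is not linked to the PFS event.
- Section 4.2 lists death as an event-monitoring item. This shows that the data will exist, not that they enter PFS.

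No section counts death as a PFS event.

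**The plan's own figures.** Section 16.112 gives the only design calculation for phase II, and it rests on response. For stop at ≤1 of 9 and promising at >5 of 23, exact binomial calculation gives:

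- early stop at a 15% response rate: 0.85^9 + 9 × 0.15 × 0.85^8 = 0.2316 + 0.3679 = 0.5995 (stated 60%)
- type I error: 0.0990 (stated limit 10%)
- power at 35%: 0.8037 (stated 80%)

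All three reproduce, and none depends on the PFS definition. The plan states no median, rate, event count or power for PFS.

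**Size of the bias.** Let λ be the hazard of the first of progression or death, and s the share of first events that are deaths without documented progression. Both are assumptions; neither is in the documents.

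- True PFS: S(t) = exp(−λt), median m = ln 2/λ.
- With deaths censored, the curve estimates exp(−(1 − s)λt) = S(t)^(1 − s), with median m/(1 − s).

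For an assumed true median of 3.0 months, true 6-month PFS is 0.5² = 25%:

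| s | Median multiplied by | Reported median (months) | Reported 6-month PFS |
|---|---|---|---|
| 10% | 1/0.9 = 1.11 | 3.3 | 0.25^0.9 = 29% |
| 20% | 1/0.8 = 1.25 | 3.75 | 0.25^0.8 = 33% |
| 30% | 1/0.7 = 1.43 | 4.3 | 0.25^0.7 = 38% |

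**Simulation at the trial's size.** This used 23 patients, 2,000 runs and scans every 6 weeks (Section 11.1: "patients should be reevaluated every 6 weeks"). Death was either counted as an event or censored at the last scan. Mean estimated 6-month PFS:

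| Assumed true median | s | Death as event | Death censored | Difference (points) |
|---|---|---|---|---|
| 3 months | 10% | 0.279 | 0.315 | 3.6 |
| 3 months | 20% | 0.272 | 0.346 | 7.4 |
| 3 months | 30% | 0.270 | 0.395 | 12.5 |
| 6 months | 10% | 0.529 | 0.564 | 3.5 |
| 6 months | 20% | 0.520 | 0.592 | 7.2 |
| 6 months | 30% | 0.518 | 0.632 | 11.4 |

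The death-as-event values lie above 25% and 50% because progression is dated at the next scan. In no run was the 6-month estimate lower with deaths censored. The estimated median moves more coarsely because of the scan spacing. At s = 10% the typical median did not change (4.14 months in both analyses for a true median of 3; 6.9 in both for 6). At s = 30% it rose from 3.59 to 4.14 and from 6.9 to 9.67 months.

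**The case against.** The strongest reply concerns reach and size. PFS is secondary, it has no hypothesis or threshold, and the stopping and success rules use confirmed response only. The Cox models are declared exploratory. All of this stands, and it limits the harm to what is reported on PFS.

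The overstatement is also conditional. Section 11.46 captures some declining patients. Patients who stop treatment for reasons other than irPD enter event monitoring (Section 13.3), with contact every 3 months until PD (Section 4.2). No section supports a share of 20% or 30%. With 23 patients, 10% is about two deaths, and the resulting shift from 25% to 29% is small beside a rough 95% half-width of 1.96 × √(0.25 × 0.75/23) = 18 points. This stands as a caution on size. It does not excuse the definition: sampling error is shown by a confidence interval, whereas this bias is not.

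Scan gaps can be argued either way. Section 11.1 gives 6 weeks, a footnote in Section 4.1 gives 12–16 weeks after Cycle 4, and Section 11.33 allows 3 months after at least 6 months of stable disease. Longer gaps leave more room for death before progression is documented, but the sections do not agree, and the conclusion does not need the longest interval. The simulation used 6 weeks.

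Finally, these deaths are not lost to the trial: they count in OS, and those within 30 days of treatment or at least possibly related to it are Grade 5 adverse events. That is correct, but it does not repair the PFS curve.

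**Conclusion.** The concern holds. As written, Section 16.3 yields time to progression labelled PFS, and it errs upward on average whenever a patient dies without documented progression. Under constant hazards the median is overstated by 11% to 43% for an assumed share of such deaths of 10% to 30%. In the simulation, mean 6-month PFS was overstated by 3.5 to 12.5 percentage points over the same range. The share and the true medians of 3 and 6 months are assumptions, and the bias is zero if no such death occurs. The RECIST and irRECIST versions of PFS and the Cox models on PFS are affected. The primary analysis, sample size, type I error and power are not. The definition should be corrected before analysis, so that the event is not chosen after the deaths are known.

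**What to change.** In Section 16.3, define PFS as the time from study enrollment to the first of RECIST 1.1 progression or death from any cause. Censor only patients who are alive without progression, at their last adequate tumour assessment. State the same rule for the irRECIST version, with irPD in place of PD. If time to progression is also wanted, give it that name and treat death as a competing event; this is optional.

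The cost is a small change of wording. Deaths are already collected for OS and under Section 4.2, so no visit, form or patient is added, and sample size, type I error and power stay the same.
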